### **13.3.2. Secondary Efficacy Analysis**

The secondary efficacy outcomes include:

- Other Gastroparesis Core Symptoms: vomiting, early satiety, post-prandial fullness, and upper abdominal pain;
- mGCSI
- mPAGI-SYM
- PGI-C
- PAGI-QOL
- GTBS
- CGI-S

Continuous endpoints will be summarized and analyzed in a manner similar to the primary endpoint. Details of the analysis will be described in the SAP.

Categorical variables will be evaluated as described in the SAP. Time to event data will be analyzed using the Kaplan-Meier method, and the treatment group differences will be tested by the log-rank test. Details of the analysis will be described in the SAP.

### **13.4. Safety Data Analysis**

The primary assessment of safety will be based on the frequency of treatment-emergent adverse events (TEAEs), serious adverse events (SAEs) and on the frequency of clinically notable abnormal vital signs, electrocardiograms (ECGs) and laboratory values. Other safety evaluations include changes in vital signs, changes in clinical laboratory evaluations, and changes in ECGs, physical exam findings during treatment, and suicide ideation and behavior events.

### 13.4.1. Adverse Events

Adverse events will be recorded throughout the study and at early discontinuation. Adverse events and medical conditions will be coded using the Medical Dictionary for Regulatory Activities (MedDRA) coding dictionary. Treatment-emergent adverse events will be defined as those events, which are newly occurring or worsening from baseline. In all cases only treatment emergent adverse events will be summarized.

Treatment-emergent adverse events will be summarized within each treatment group by primary system organ class (SOC) and preferred term. (**NOTE**: In any given category [e.g. body system] a subject will only be counted once.) The incidence rates of TEAEs will be analyzed as described in the SAP. Similar displays will be provided for SAE and prior (conditions ending prior to the first dose of study medication and current (conditions present while on study medication) medical conditions.

Adverse events will further be categorized by severity, relationship to study medication, and action taken. Other information collected will be listed, as appropriate. Any event starting more than 3 days after the final dose of study medication will be excluded from the above tables and only listed, unless the event caused discontinuation.

The proportions of subjects experiencing SAEs and AEs resulting in discontinuation from the study will be summarized by treatment groups.

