### 11.1.7.3. Adverse Event Follow-Up

Subjects with non-serious AEs that are ongoing at the subject’s last study visit must be followed until resolution or for 30 days after the subject’s last study visit, whichever comes first. Non-serious AE that are reported during the 7 days following the subject’s last study visit will be recorded on the Adverse Events CRF and followed until resolution or for up to the 30 days after the subject’s last study visit, whichever comes first. SAEs will be followed until the event resolves or the event or sequelae stabilize. SAEs that are reported within 30 days of the subject’s last study visit should be reported as indicated in [Section 11.1.10](#).

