### 11.1.7.4. Adverse Event Reporting Period

AEs are to be recorded in the source documents from the time of the subject’s informed consent signature until the end of the subject’s study participation. Each AE, both serious and non-serious, will also be reported on the Adverse Events CRF. CRF Completion Instructions will be provided to each investigational site. If the subject reports or the Investigator learns of a new AE(s) up to 7 days after the subject’s last study visit or a new SAE(s) up to 30 days after the subject’s last study

visit, the investigational site personnel will ensure that these data are recorded on the Adverse Events CRF for the study. The period during which an SAE must be reported may be extended if there is a strong suspicion that the event being reported is related to the study medication or a study procedure.

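### By-arm SAE tables stop 3 days after the final dose while SAEs are collected for 30 days after the last visit, so the tables and the unwindowed SAE proportion can disagree

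*Combined protocol and SAP*

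**What the plan says.** Section 13.4.1 first plans treatment-emergent event tables within each arm by system organ class and preferred term, and adds: "Similar displays will be provided for SAE". The cut-off comes after these displays: "Any event starting more than 3 days after the final dose of study medication will be excluded from the above tables and only listed". It has one exception: "only listed, unless the event caused discontinuation". A separate paragraph then says: "The proportions of subjects experiencing SAEs and AEs resulting in discontinuation from the study will be summarized by treatment groups". That sentence has no time window.

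Two other sentences in the section bear on the window. One limits the summaries: "In all cases only treatment emergent adverse events will be summarized". The other defines the term: "Treatment-emergent adverse events will be defined as those events, which are newly occurring or worsening from baseline". The definition sets a start but no end.

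Collection runs longer. Section 11.1.7.4 has sites record on the CRF any new AE learned of up to 7 days after the subject's "last study visit or a new SAE(s) up to 30 days after the" same visit. It allows an extension where a link to study medication or a study procedure is strongly suspected. Section 11.1.7.3 uses the same period in its reporting instruction ("SAEs that are reported within 30 days of the subject"). Section 13.4 makes SAE frequency part of the primary safety assessment.

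**The concern.** The plan collects SAEs for about a month after the last visit, but its SAE breakdown by arm ends 3 days after the last capsule. No visible text reconciles the two. A reader of the report could find an SAE proportion by arm that does not match the SAE table by arm, with no rule to explain the difference.

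This affects the randomized comparison mainly through two groups. Early discontinuers do not meet the entry criterion of the open-label extension (Section 20.1.4.1). Completers who finished before the extension opened return, if at all, at Visit 4a (Section 5.1.3). Other completers receive open-label drug at Visit 4 (Section 9.1.4) and have essentially no off-drug period. Because discontinuation happens after randomization and may differ between arms, a count by arm is useful for that group.

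**Working it through.** The plan gives no figure on this point to reproduce, so the check compares the text and then does the window arithmetic.

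**Text**

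1. The SAE displays are announced before the exclusion sentence, so they are among the tables it restricts.
2. The exception does not rescue a post-visit event. Section 6.3 defines discontinuation as leaving the study before all scheduled evaluations are done. An event starting after a subject's last visit cannot cause that.
3. The proportion sentence follows the exclusion, which refers back to the tables, so the 3-day rule does not clearly apply to it. It has two readings:
   - Two items, SAEs and AEs leading to discontinuation (the more natural reading). Late SAEs enter the overall proportion but not the tables.
   - Only SAEs and AEs that led to discontinuation. Late SAEs then have no by-arm AE summary.
4. The treatment-emergent limit does not decide between these, because the definition has no end date.
5. Deaths while in the study still appear by arm as a discontinuation reason (Sections 6.3 and 13.2.3). Deaths after the last visit do not.

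**Days outside the tables**

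Let g be the days from last dose to last visit. The documents do not give g, so 0 and 3 are assumed.

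Post-visit collection days outside the tables = 30 − max(0, 3 − g)
- g = 0: 27 of 30 (90%)
- g = 3: 30 of 30

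Whole window from first dose = day of last dose + g + 30. Days outside = whole window − day of last dose − 3.

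| Last dose | g = 0 | g = 3 |
|---|---|---|
| Day 28, no roll-over | 27/58 = 47% | 30/61 = 49% |
| Day 14 | 27/44 = 61% | 30/47 = 64% |

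These are shares of calendar time, not of events.

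**Expected number of subjects**

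There are 75 subjects per arm (Section 13.1). Let f be the share not rolling over directly and r the 28-day SAE risk. Both are assumptions, as are full ascertainment and the same risk off drug as on drug.

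Expected per arm = 75 × f × [1 − (1 − r)^(27/28)]
- f = 0.1, r = 0.01: 0.07
- f = 0.2, r = 0.03: 0.43
- f = 0.3, r = 0.05: 1.09

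Each such subject with no earlier SAE adds 1/75 = 1.3 percentage points to the arm's SAE proportion.

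**Counting time if all collected SAEs are shown (g = 0)**

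A roll-over completer counts for 28 days, a Day 14 withdrawer for 14 + 30 = 44, and a completer who does not roll over for 28 + 30 = 58. Assume 10% of one arm and 30% of the other do not roll over.
- All of them Day 14 withdrawers: 0.1 × 44 + 0.9 × 28 = 29.6 days against 0.3 × 44 + 0.7 × 28 = 32.8 days, ratio 1.11
- All of them completers: 0.1 × 58 + 0.9 × 28 = 31.0 days against 0.3 × 58 + 0.7 × 28 = 37.0 days, ratio 1.19

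**The case against.** The strongest reply is that the 3-day rule is an explicit on-treatment choice. Collecting for longer than one tabulates is not a contradiction, and no data are lost because later events are listed. This stands, and it is why the 3-day tables should stay. It does not answer the missing window for the proportion, and a listing gives no count by arm.

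Second, the natural reading of the proportion sentence already yields an overall by-arm count of all SAEs. This also stands. A reader might infer that late SAEs vanish from every by-arm summary, but that follows only on the narrower reading.

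Third, a reader might take the 47% to 64% shares as the fraction of SAEs lost. The documents do not support that. Capture after the last visit is passive: it depends on the subject reporting or the investigator learning of an event, and no scheduled contact is visible for subjects who do not roll over. Days after the visit are therefore not equivalent to days covered by visit queries.

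Fourth, Section 13.2 leaves full detail to an SAP, and the combined document as supplied shows no separate SAP text. The window for the proportion may be set there. Section 11.1.9.2, on post-study adverse events, is not visible either, so the point rests on Sections 11.1.7.3, 11.1.7.4 and 13.4.1. The 3-day rule itself, however, is stated without deferral.

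Fifth, a reader might infer that the final dose means the last open-label dose, because Section 20.1.5.1 uses the same term, study medication, for the open-label capsules. Context favours the double-blind dose: the summaries are by treatment group, and each extension has its own statistical section. This needs clarification only.

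**Conclusion.** The point holds as a reporting gap. Followed as written, Section 13.4.1 removes collected late SAEs, including deaths after the last visit, from the by-arm breakdown by system organ class and preferred term. It also leaves the overall SAE proportion without a window, so the two can disagree.

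The size is small. Under the assumed ranges (10% to 30% not rolling over, 1% to 5% SAE risk per 28 days), at most about one subject per arm is affected, and the lower end is well under one. The documents give no rates to narrow this. It would be wrong to conclude that SAE data are lost or that the trial's safety conclusion is in doubt. This is a cheap improvement to the reporting of a primary safety measure and is worth making before database lock.

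**What to change.** - Keep the 3-day on-treatment tables, and state that the final dose means the last double-blind dose.
- State that the SAE proportion covers all SAEs, and give its window.
- Add one supplementary by-arm display of all collected SAEs and deaths, from the first double-blind dose to the end of the 30-day period or the first open-label dose, whichever is earlier. Show counting time by arm beside it and label it descriptive.

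The cost is one display, one definition and one clarifying sentence, from data already collected. Section 13.2 lets changes in statistical methods before database lock be documented in the SAP without a protocol amendment.

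The display has limits that should be stated with it. Some unrelated off-drug events will be counted. Counting time depends on disposition, with the 1.11 to 1.19 ratio between arms shown above. Post-visit events are passively ascertained, and showing counting time does not correct for that.

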### **5.1.3. Open-Label Extension Phase**

All subjects who complete the short-term double-blind phase will continue treatment with tradipitant for an additional 8-weeks of treatment in the OLE phase. Subjects who have completed the trial prior to the OLE becoming available can come back and sign an additional informed consent and be evaluated for eligibility to participate in this phase during V4a. The site will record that the subject has completed the double-blind phase of the study and indicate if the subject will continue into the OLE. If the subject will continue into the OLE, enough open label medication will be dispensed to the subject to last until the next schedule visit. Patients who have previously completed this study can come back to for visit V4a to allow all original V1 screening labs and other safety assessments as well as the open label informed consent to be collected prior to OLE dosing.

A detailed description of this OLE phase can be found in [Appendix 20.1](#)

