**9.1.4. Visit 4 (Study Day 28 ± 3 days)**

- Full PE (excluding pelvic, rectal and breast examinations unless clinically indicated)
- Laboratory evaluations (HbA1C, hematology, chemistry (including eCLcr; based on the Cockcroft-Gault equation), urinalysis, thyroid stimulating hormone (TSH), thyroxine (T4), and urine drug screen)
- Serum pregnancy test and collection of menstrual cycle information (for females of child-bearing potential)
- Pharmacokinetic blood sample
- ECG
- Semi-supine routine vital signs (body temperature, respiratory rate, blood pressure, and pulse) and weight
- Adverse Event query
- Concomitant medication review
- Since last visit C-SSRS
- Review diary
- Collect diary
- Modified Gastroparesis Cardinal Symptom Index (mGCSI)
- Modified PAGI-SYM (mPAGI-SYM)
- Patient Global Impression of Change (PGI-C)
- Patient Assessment of Upper Gastrointestinal Disorder Quality of Life (PAGI-QOL)
- Clinical Global Impression of Severity (CGI-S)
- Study medication collection and review
- Records EOP
- Review of Inclusion criteria (only for subjects that are continuing to the OLE phase)

- Dispense Study Drug (only for subjects that are continuing to the OLE phase)

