### **13.2.6. Prior/Concomitant Therapy**

Any medications or therapy present before the first dose of study medication (Visit 2) will be considered as prior medications. Concomitant medications (medications present while on study medication) will be recorded throughout the study and at early discontinuation. These medications will be coded using the WHO-drug dictionary. The number of subjects from the Safety Population using prior or concomitant medications will be categorized by the WHO-drug category and preferred term, and presented for each treatment group. In any given category (e.g., drug category) a subject will be counted only once.

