#### **20.1.2. Phase Rationale**

#### **20.1.3. Study Design for OLE Phase**

The OLE phase consists of an additional 8-weeks of treatment where all subjects will receive the same daily dose of tradipitant in an open-label fashion. Subjects who received tradipitant during the evaluation phase will continue to receive tradipitant. Subjects who received placebo during the evaluation phase will also receive tradipitant.

Subjects will go to the clinic during the OLE on the days specified in the Schedule of Evaluations for OLE ([Table 8](#)) for routine safety assessments which may include a urine pregnancy test for women of child-bearing potential (WOCBP), urine drug screen, vital signs measurements, safety labs, physical exam, an ECG and collection of adverse event including suicidality ideation and behavior and concomitant medication information. Refer to [Table 8](#) and [Section 20.1.10](#) for details of which assessments are done per Study Visit. Study medication will be dispensed at some of these visits and compliance will also be assessed. End-of-study (EOS) assessments and an additional gastric emptying breath test will be performed at Visit 6 (Study Day  $84 \pm 3$  days) or at the time of early discontinuation. EOS assessments include safety evaluations such as serum pregnancy test for females, physical examination (PE), vital signs, ECG, collection of adverse event including suicidality ideation and behavior and clinical laboratory assessments ([Table 8](#)).

Visit	V4a	V5	V6 EOP
Study Day		Day 56	Day 84
Study medication collection & compliance		X	X
EOP			X

 Only for subjects that completed the Double-Blind Phase prior to the OLE being available.

 within +/- 3 days

 Adverse event collection will begin at the time the ICF is signed.

 Vital sign collection at all visits. Height collection at V1 only.

 The Screening/Baseline C-SSRS will occur at V1. The Since Last Visit C-SSRS will occur at all other visits.

EOS = End of Study; ET = Early Termination; WOCBP = Women of Child-bearing Potential; ECG = electrocardiogram; C-SSRS = Columbia Suicide Severity Rating Scale

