### 20.1.5. Study Medication

#### 20.1.5.1. Dosing

Subjects will be dispensed study medication under open-label conditions at the study visits indicated in the Schedule of Evaluations for OLE ([Table 8](#)). Subjects will be instructed to take one capsule of study medication every day in the morning, and one capsule of study medication every day in the evening approximately 12 hours later. Each capsule will contain either 85 mg of tradipitant.

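### The by-arm adverse-event tables do not stop at the first open-label dose, so up to 3 days of tradipitant can be counted under placebo

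*Combined protocol and SAP*

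**What the plan says.** Section 13.4.1 (Adverse Events) defines treatment emergence against baseline only: "Treatment-emergent adverse events will be defined as those events, which are newly occurring or worsening from baseline". It summarizes these events, and SAEs in similar displays, within each treatment group. One sentence closes the window: "Any event starting more than 3 days after the final dose of study medication will be excluded from the above tables", with the exception "unless the event caused discontinuation". The sentence does not say which phase's final dose is meant.

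Other sections describe what happens at the end of the double-blind phase:

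- Section 5.1.3: "All subjects who complete the short-term double-blind phase will continue treatment with tradipitant for an additional 8-weeks".
- Section 20.1.3: "Subjects who received placebo during the evaluation phase will also receive tradipitant".
- Section 9.1.4, in the list of Visit 4 procedures: "Dispense Study Drug (only for subjects that are continuing to the OLE phase".
- Section 20.1.5.1 uses the same term for the open-label drug: "Subjects will be dispensed study medication under open-label conditions".

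Sections 13.2.3 (disposition) and 13.2.5 (noncompliance) restrict their by-arm summaries to the double-blind phase. Section 13.4.1 does not.

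**The concern.** A post-dose tail of a few days is a normal way to catch late reactions when subjects come off drug. Here many subjects do not come off drug. A placebo completer who rolls over at Visit 4 starts tradipitant inside the tail, and an event that begins then is counted against placebo.

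The two arms are not affected alike. For a placebo subject, the extra days are the first days ever on tradipitant. For a tradipitant subject, they are roughly days 29 to 31 of continuous exposure. The placebo column therefore takes in first-exposure events, and the comparison is pulled toward no difference.

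The waiver has no time limit. Section 6.3 defines discontinuation as leaving the study before all scheduled evaluations are done. Read literally, an open-label event that led to withdrawal could therefore enter the by-arm tables whenever it began.

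Section 13.4 makes the frequency of treatment-emergent and serious events part of the primary assessment of safety, and the 4-week double-blind phase is where this protocol compares that frequency with placebo.

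**Working it through.** The plan gives no adverse-event rate, so it has no figure of its own to reproduce on this point. (The 86% power in Section 13.1 concerns nausea severity and is not affected.)

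**Inputs from the documents.** Double-blind phase 28 days; tail 3 days; 75 subjects per arm; open-label drug dispensed at Visit 4 to those continuing.

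**Share of the placebo window, narrow reading (final double-blind dose + 3 days).**

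- Per direct rollover: 3 / (28 + 3) = 3/31 = 9.7%.
- Whole arm, if all 75 roll over at once: 75 × 3 = 225 tradipitant days against 75 × 28 = 2,100 double-blind days; 225 / 2,325 = 9.7%. This is the ceiling.
- If only a fraction d rolls over directly, the share is about 3d/31, ignoring the shorter windows of dropouts. The documents do not give d. Assuming d = 0.75 gives 2.25/31 = 7.3%; d = 0.50 gives 1.5/31 = 4.8%.

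**Effect on the columns.** Let p0 and p1 be the 28-day risks on placebo and tradipitant. These are assumptions. Take constant hazard, all subjects rolling over, and 3 further tradipitant days in both arms:

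- Placebo column = 1 − (1 − p0)(1 − p1)^(3/28)
- Tradipitant column = 1 − (1 − p1)^(31/28)
- Difference = (p1 − p0) × (1 − p1)^(3/28)

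With p0 = 2% and p1 = 10%:

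- 0.90^(3/28) = 0.989
- Placebo column = 1 − 0.98 × 0.989 = 3.1%
- Tradipitant column = 1 − 0.90 × 0.989 = 11.0%
- Difference = 8.0 × 0.989 = 7.9 points, against 8.0
- Ratio: about 3.6, against 10/2 = 5.0

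| Assumed 28-day risks (placebo / tradipitant) | Columns as tabulated | Difference (true) | Ratio (true) |
|---|---|---|---|
| 2% / 10% | 3.1% / 11.0% | 7.9 (8.0) | 3.6 (5.0) |
| 5% / 10% | 6.1% / 11.0% | 4.9 (5.0) | 1.81 (2.0) |
| 5% / 20% | 7.2% / 21.9% | 14.7 (15.0) | 3.02 (4.0) |
| 10% / 20% | 12.1% / 21.9% | 9.8 (10.0) | 1.81 (2.0) |

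Under constant hazard both columns rise almost equally, so the risk difference is nearly preserved and the ratio carries the distortion. If the hazard on tradipitant is highest just after the first dose, the placebo column gains more than the tradipitant column and the difference shrinks too. The documents give no onset times, so I put no number on that.

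**The case against.** The strongest reply is that the tables in Section 13 are meant for the randomized phase. Sections 20.1.13 and 20.2.14 give each extension its own exploratory summaries, laid out like those of the randomized phase, and Section 13.2.1 sets the efficacy endpoint within the evaluation phase. This largely answers a stronger reading that a reader might infer: because open-label drug is also called study medication, the cut-off would run to the last open-label dose and sweep the whole extension into the placebo column. That is possible on the bare words but unlikely to be intended, and I do not size the problem on it. What the reply leaves untouched is the 3-day overlap, which arises when the cut-off is taken from the final double-blind dose. No text assigns an event to a phase.

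A second reply is that detail is deferred. Section 13.2 describes the methods as general, and Section 13.4.1 leaves the analysis of incidence rates to the SAP. No separate SAP text is in the documents supplied. But the window itself is stated in Section 13.4.1, not deferred.

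Third, not every completer rolls over without a gap. Sections 5.1.3 and 20.1.10.1 provide for subjects who finished before the extension opened and return at Visit 4a; they overlap only if the gap is under 3 days. The site also records whether a subject will continue. This stands, and it is why 9.7% is a ceiling.

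Fourth, it is tempting to claim that the difference between arms shrinks sharply. The documents do not support that: it needs an assumed clustering of onsets for which they give no data.

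On the waiver, one can argue that a subject who completed the double-blind phase has not discontinued from it. That is a reasonable reading, but Section 13.4.1 speaks of discontinuation from the study.

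**Conclusion.** The point holds in a limited form. As written, the rule in Section 13.4.1 counts events from up to the first 3 days of open-label tradipitant under placebo, for placebo subjects who go directly into the extension. The overlap is at most 3 of 31 days per subject (9.7%), and smaller across the arm by an amount the documents do not allow one to state. Under constant hazard and the assumed risks above, differences fall by 0.1 to 0.3 points, while ratios fall from 5.0 to about 3.6, from 4.0 to 3.02, and from 2.0 to 1.81. A material loss in the difference requires onsets concentrated just after the first dose. The waiver could add open-label withdrawals if read literally; its contribution cannot be sized.

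Safety is an exploratory secondary objective of this phase IIa study. The distortion nevertheless makes the drug look more like placebo, and it is easily removed, so it should be corrected before database lock.

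**What to change.** In Section 13.4.1, or in the SAP:

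- End each subject's double-blind AE and SAE window at the earlier of the first open-label dose or 3 days after the last double-blind dose.
- Apply the discontinuation waiver only to events that start before the first open-label dose.
- Tabulate later events in the OLE and COLE summaries as on-tradipitant events, by original arm.
- State how an event dated on the day of the first open-label dose is assigned.

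The cost is a few lines of wording and one date comparison per event, with no new data. Section 13.2 allows changes in statistical methods before database lock to be documented in the SAP without a protocol amendment. The downside is that a few late-onset events arising from the double-blind phase will appear in the OLE tables instead; showing those tables by original arm keeps them visible.
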